11.1.3 Geriatric assessment: Medians and frequencies will be used to describe the baseline characteristics of participants and performance on the CGA. Overall survival and associated 95% CI will be estimated as in Aim 1 and correlated with CGA measures. Cox proportional hazards models will be fit for each CGA measure as a predictor of OS, in unadjusted models and models controlling for age, gender, and ECOG score. We also will estimate the hazard ratios in adjusted Cox regression models for continuous variables. To assess the incremental impact of cognitive and physical function variables on predicting survival, we will use Integrated Discrimination Improvement as described for survival analysis by Chambliss et al.[41] and implemented in the RiskPredictionParams SAS Macro (macro version 8, Chapel Hill, NC). The variables included in the model will be those associated with survival in our analysis and included in Kantarjian's predictive model for early mortality[42]. Internal cross-validation of the model will be assessed using 1000 bootstrap replicates implemented in the RiskPredictionParams SAS macro. Logistic regression analysis will be used to investigate relationships between baseline CGA and exploratory outcomes of 30-day mortality and CR. Competing risk modeling will be used to investigate a differential effect of impairment in CGA measures by cause of death[43].

For correlative studies, probe ID's on Affymetrix U133A gene chip have been identified for the candidate cytokines and include: IL-6 (211000,

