2055207, 204864, 204863, 205945, 212196), IL-1 (39402, 205067, 10118, 208200, 201404, 216245), IL-2 (207849, 204116), TNF- α (211841, 211282, 210405, 211495, 211153, 207643, 207849), and CRP (207849, 204116). The mean value for each cytokine from the Luminex assay will allow us to identify patients with high or low levels of each cytokine, and relate them to genetic typologies. Correlations between the serum cytokine levels and mRNA gene expression level for the cytokines will be evaluated by Spearman correlation. Specifically, the range of genes will be related to the panel of cytokines. Statistical significance will be assessed controlling for Type-I error using Hochberg tests, which are less conservative relative to the more common Bonferroni corrections[44, 45]. In order to reduce the dimensionality of the problem further, in follow-up tests, we will assess if factorization of the cytokines is feasible (using Principal Components Analysis (PCA)), and, if so, the resulting components will be related to the genetic typologies. We note that skew will likely be present in the cytokine panel which can impact the factorization above. We will assess skew, and, if necessary, transform the variables individually to bring about approximate normality. All analyses will be conducted at a two-sided α -level of 0.05 using SAS statistical software, version 9.2 (SAS Institute Inc., Cary, NC). We will use Spearman's correlation to assess the relationship between the biologic markers (serum cytokines and gene expression values) and clinical markers (each domain on the CGA and ECOG PS). While this work is exploratory and it could be argued that there is no need to adjust for multiple testing we will adjust p-values by the Hochberg method to control the Type-I error rate inherent in multiple testing[46]. All statistical analyses will be conducted in conjunction with our co-investigator, [name].

11.2 Secondary Objectives:

11.2.1 Evaluate incidence and severity of acute GVHD.

In addition to monitoring the rate of grade III-IV aGVHD of the gut or liver and grade IV aGVHD of the skin as in 10.1.1, we will also monitor overall rates of GVHD. Rates will be calculated with one sided 85% confidence interval.

11.2.2 Evaluate incidence and severity of other adverse events.

We will monitor other adverse events as defined in sections 7.0 and 9.0. Rates will be calculated with one sided 85% confidence interval.

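### In the exploratory gene-expression correlatives of section 11.1.3, the probe IDs printed for CRP are identical to those for IL-2, so the list cannot tell the two apart

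*Combined protocol and SAP*

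**What the plan says.** The correlative part of section 11.1.3 states that probe IDs on the U133A chip "have been identified for the candidate cytokines and include" five lists, one each for IL-6, IL-1, IL-2, TNF-alpha and CRP. The IL-2 list is "IL-2 (207849, 204116". The CRP list is "and CRP (207849, 204116". The seven-entry TNF-alpha list ends in "211153, 207643, 207849".

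Two analyses draw on expression values:

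- Serum cytokine levels are correlated, by Spearman's method, with the "mRNA gene expression level for the cytokines". The plan then adds that "the range of genes will be related to the panel of cytokines".
- Biologic markers are correlated with clinical ones: "serum cytokines and gene expression values) and clinical markers (each domain on the CGA and ECOG PS".

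P-values are to be Hochberg-adjusted, and the plan describes the status of the work in the clause "While this work is exploratory".

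Section 6.4.7, in its paragraph on biologic markers, names the same five serum markers and explains that a probe set's signal measures one gene's expression. It gives no probe list. Section 6.4.2 cites a separate laboratory manual for the correlative studies, which is not among the documents supplied.

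**The concern.** The list is the only place in the documents that ties a cytokine to its array measurements. Two cytokines with identical lists cannot have two different expression variables. An analyst who followed the list cytokine by cytokine would report a CRP mRNA association that repeats the IL-2 one number for number, and a reader could take the repeat for independent support. Serum CRP and serum IL-2 would also be compared with the same expression values, so neither comparison could be said to concern that cytokine's own transcript. CRP and IL-2 are two of the five candidate markers, and the introduction gives validation of the CGA against cytokine and genomic profiles as an aim.

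**Working it through.** The plan gives no count or summary figure to reproduce, so the check is a comparison of the five printed lists in section 11.1.3.

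| Cytokine | Printed IDs | Entries | Found in no other list |
|---|---|---|---|
| IL-6 | 211000, 2055207, 204864, 204863, 205945, 212196 | 6 | 6 |
| IL-1 | 39402, 205067, 10118, 208200, 201404, 216245 | 6 | 6 |
| IL-2 | 207849, 204116 | 2 | 0 |
| TNF-alpha | 211841, 211282, 210405, 211495, 211153, 207643, 207849 | 7 | 6 |
| CRP | 207849, 204116 | 2 | 0 |

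1. Entries printed: 6 + 6 + 2 + 7 + 2 = 23.
2. Repeats: 207849 appears 3 times (IL-2, TNF-alpha, CRP), which is 3 − 1 = 2 surplus entries. 204116 appears twice (IL-2, CRP), which is 2 − 1 = 1 surplus entry.
3. Distinct IDs: 23 − 2 − 1 = 20.
4. Overlap: IL-2 and CRP share 2 of 2 IDs, TNF-alpha shares 1 of 7, and IL-6 and IL-1 share none.

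What follows depends on how expression is paired with cytokines, which the plan does not state outright:

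- **Each cytokine with its own list.** The input for CRP is {207849, 204116} and the input for IL-2 is {207849, 204116}. Whether the two probe sets are combined or tested separately, the expression values are the same, and so is every coefficient against a given clinical marker.
- **Every probe set with every serum cytokine.** Each of the 20 distinct probe sets gives one coefficient per serum cytokine, and the repetition changes none of them. Only the naming is affected: 207849 sits under three headings and 204116 under two, so results for these two probe sets cannot be attributed to one cytokine heading.

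Could this come from reading the PDF? A reader may garble a digit or break a table. It is unlikely to reproduce an exact pair of six-digit numbers, in the same order, under a second label in running text. Nothing at this place is redacted, and no other supplied text gives a different list.

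**The case against.** The best case against the point is that the plan's more specific sentence relates the whole range of genes to the whole cytokine panel. That favours all-by-all pairing, under which no coefficient changes. The list is also introduced with a word that need not mean it is complete, so further IDs for CRP or IL-2 may exist. The laboratory manual may hold a correct working list. This much stands: the duplicated-variable consequence is conditional on own-list pairing and on the list being used as printed.

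Two stronger readings are tempting, and the documents support neither.

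- A reader might infer that at least 3 of the 23 entries are wrong (2 + 1 surplus entries, if each probe set measures one gene and each list holds only that cytokine's own gene). The second condition is not established. The phrase about a range of genes leaves room for related genes. Section 6.4.7 can also be read as one probe set per gene, yet three of the lists hold six or seven IDs. If related genes were intended, an ID under two headings is overlap and need not be a conflict of gene labels.
- A reader might count how many CGA and ECOG coefficients would be duplicated. That count needs one score per CGA domain, one sampling time and a complete list. Section 6.4.7 puts several instruments in some domains and lists several sampling times, and no scoring rule is given.

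What survives is narrower. None of these readings explains why CRP and IL-2 have exactly the same two IDs and nothing else.

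**Conclusion.** The concern holds as a low-priority correction to an exploratory analysis. As printed, CRP and IL-2 have no probe set that separates them: 0 of 2 IDs are unique for each, against 6 of 6 for IL-6 and IL-1 and 6 of 7 for TNF-alpha. With own-list pairing the two expression variables are one variable. With all-by-all pairing the numbers stand, and only the attribution of two of the 20 distinct probe sets is unclear.

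The conclusion rests on the list as printed. The documents do not show which gene either ID represents or which entry is wrong, and none is named here as the error. The toxicity stopping rule, the 1-year DFS test and the CGA survival models do not use the list and are unaffected. No meaningful effect on the Hochberg thresholds is claimed.

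**What to change.** Before the correlative analysis is run:

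- Check all printed IDs against the U133A annotation file and record the annotated gene for each distinct probe set. The same look-up can confirm the three IDs that do not have six digits (2055207, 39402, 10118); no error in them is asserted.
- Correct the CRP, IL-2 and TNF-alpha lists. If the array has no probe set for CRP or for IL-2, drop that mRNA correlation.
- If related genes are intended, say so. In either case, report results by annotated gene name, not by cytokine list.
- State whether each cytokine is paired with its own probe sets or with all of them, and count each distinct probe set once in the Hochberg family.
- If the laboratory manual cited in section 6.4.2 already holds a correct list, refer to it in section 11.1.3.

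The cost is one look-up and a short correction to the text. No new sample, assay or visit is needed, because the chip is scanned whatever the list says.

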6.2.3 Storage and processing

The stem cells are processed in the Duke University Medical Center Stem Cell Laboratory and infused to the donor following the standard laboratory procedures for allogeneic stem cell infusions. Freshly collected cells will be used in the first course of treatment and donor cells will be divided into aliquots and cryopreserved in liquid nitrogen for subsequent infusions. Each infusion of the cells will be performed 1 day following each chemotherapy regimen and that day will be counted as 'day 0'. The target dose of CD3+ cells is 1×10^8 cells/kg (the collection goal of 3×10^8 CD3+ cells/kg is to obtain 1 aliquot of 1×10^8 CD3+ cell/kg for each of induction and consolidation2, with 1×10^8 CD3+ cell/kg saved in case of need for re-induction). If only $2-3 \times 10^8$ CD3+ cell/kg is collected, then cells will only be given with IND1 and CON2 (IND2 may still be done, but cells will not be given). We will also monitor the total number of mononuclear, CD34+, CD3-CD16+CD56+ (NK) cells, CD3+CD16+CD56+ (NKT) cells, and gamma-delta T-cells infused, but the infusion dose will be calculated around CD3+ population.

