6.4.4 Evaluation of immune function

We will evaluate immune function based peripheral blood and bone marrow analysis using the following assays:

1. Cytokines will be measured, particularly levels of IL1, IL1beta, CRP, IL2, IL6, IL8, IL15, IL21, IFN-gamma, TNF-alpha, TGF-beta
2. Lymphocyte subsets will be analyzed using flow cytometric lymphocyte immunotyping with fluorochrome conjugated monoclonal antibodies to CD3, CD4, CD8, CD11c, CD16, CD19, CD25, CD28, CD45RA/RO, CD56, CD57, CD62L, CD107, CD123, TCR gamma-delta, FOXP3, HLA, and KIR
3. Quantification of recent thymic immigrants will be determined by the presence of TCR rearrangement excision circles (TREC), retrospectively performed by real-time quantitative-PCR of DNA collected from an isolated fraction of CD31 T cells and next

generation sequencing to analyze diversity in the TCR repertoires produced by the rearrangements of the variable region genes.

4. NK activity will be assessed by FACS (CD56+CD107+).
These assays will be done at count recovery prior to each new cycle of therapy, at 8 weeks after the last round of consolidation, and every 3 months after completing therapy for up to two years.
Additional blood will not be drawn for this testing.

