11.2.3 Evaluate efficacy with respect to disease response and survival.

Additional efficacy endpoints include response rate, DFS, EFS, and OS. The response rate will be calculated with one sided 85%

Chemo with Adoptive Haplo DLI

confidence interval. DFS, EFS, and OS will be estimated using the method of Kaplan and Meier.

11.2.4 Evaluate immune recovery.

Immune reconstitution results will be tabulated and recorded. For the evaluation of recovery of immune function post-engraftment, we will use descriptive statistics of cytokine profiles, lymphocyte and NK enumeration and flow-based assays and make patient-specific plots of immune function parameters across time. These measurements will be performed prior to induction, prior to each round of consolidation, 8 weeks after the last cycle of consolidation, and every 3 months after treatment for up to 2 years. Specifically, we will:

1. monitor leukocyte subsets using flow cytometry:
 - CD3+
 - CD4+
 - CD8+
 - regulatory (CD4+, CD25+, CD62L+)
 - cytotoxic/late memory (CD8+, CD57+, CD28-) and activated (CD8+, HLADR+) T cells
 - naïve CD4+ T cells with L-selectin expression (CD4+, CD45RA+/CD45RO-, CD62L+)
 - gamma-delta T cells
 - B cells (CD19+, CD3-, CD16-, CD56-)
 - natural killer cells (NK) (CD3-, CD16+/CD56+, CD107+)
 - natural killer T cells (NKT) (CD3+, CD16+/CD56+, CD107+),
 - plasmacytoid dendritic cells (DCs) (CD123+, CD11c-)
 - myeloid DCs (CD123-, CD11c+)
2. quantify recent thymic immigrants by the presence of TCR rearrangement excision circles (TREC) performed by real-time quantitative-PCR of DNA collected from an isolated fraction of CD31 T cells
3. perform next generation sequencing of TCR gene rearrangements to analyze diversity in the TCR repertoires produced by the rearrangements of the variable region genes.
4. in vitro assays of NK function (measure CD16 expression, intracellular CD107a degranulation and cytokine secretions of IFN γ and TNF α after 4 hour co-culture with an effector:target ratio of 2:1)
5. measure immunoglobulin levels as a function of B-cell activity and recovery

Chemo with Adoptive Haplo DLI

6. measure cytokine levels, particularly IL1, IL1-beta, IL2, IL6, IL8, IL15, IL21, IFN-gamma, TNF-alpha, TGF-beta, CRP
7. microchimerism monitoring to determine the level of donor cells (as well as the presence of any pre-existing maternal-fetal microchimerism)
8. KIR typing to determine the effect of KIR ligand mismatch
9. PD1/PDL1/PDL2 expression (marker of T cell exhaustion)

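### Section 11.2.4 promises NK enumeration but defines NK and NKT cells as CD107+, so read literally the recovery counts mix cell number with activation

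*Combined protocol and SAP*

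**What the plan says.** Section 11.2.4 (immune recovery, a secondary objective under 2.2.4) plans "descriptive statistics of cytokine profiles, lymphocyte and NK enumeration and flow-based assays", together with plots for each patient over time. Item 1 lists the leukocyte subsets to be followed by flow cytometry. The NK entry is "natural killer cells (NK) (CD3-, CD16+/CD56+, CD107" and the NKT entry is "natural killer T cells (NKT) (CD3+, CD16+/CD56+, CD107"; in both, CD107 carries a plus sign.

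Three other places bear on this:

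- Section 11.2.4 item 4 is a separate functional assay, "in vitro assays of NK function (measure CD16 expression, intracellular CD107a degranulation" and cytokine secretion, read after a 4-hour co-culture with target cells.
- Section 6.4.4 item 4 states "NK activity will be assessed by FACS (CD56+CD107", again with a plus sign on CD107. No CD3 condition is given.
- Section 6.2.3 monitors the content of the infused product as "CD3-CD16+CD56+ (NK) cells, CD3+CD16+CD56+ (NKT) cells, and gamma-delta T-cells infused". CD107 is not part of either definition.

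**The concern.** An enumeration should count every cell of a given type. An activation marker in the definition leaves out cells that are present but not active when sampled. The protocol's own use of CD107 puts it on the activity side, yet item 1 has no NK or NKT entry without it. A reader of the recovery tables would take the NK line as a cell count, when by the written rule it is a count of CD107+ cells only.

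Two smaller inconsistencies go with this. The same cell names carry different definitions in 6.2.3 and 11.2.4. The 6.4.4 item 4 gate, as written, does not exclude CD3+ cells, so it does not separate NK from NKT cells.

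What is at stake is the meaning of one set of descriptive results. NK alloreactivity is one of the mechanisms the protocol proposes (sections 1.0, 3.5 and 4.0), so these results are likely to be read with interest.

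**Working it through.** The plan gives no numerical target for NK recovery, so there is no figure to reproduce. The check sets the definitions side by side and then works out what the literal rule counts. I take CD107 in item 1 and CD107a in item 4 to be the same marker.

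**Definitions**

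| Place | Purpose | NK | NKT |
|---|---|---|---|
| 6.2.3 | content of infused product | CD3-, CD16+CD56+ | CD3+, CD16+CD56+ |
| 11.2.4 item 1 | subset monitoring | CD3-, CD16+/CD56+, CD107+ | CD3+, CD16+/CD56+, CD107+ |
| 6.4.4 item 4 | NK activity | CD56+, CD107+ (no CD3 condition) | not mentioned |
| 11.2.4 item 4 | NK function in vitro | CD107a as degranulation read-out | not mentioned |

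**Is item 1 a counting rule?** Its other entries are signed phenotypes: B cells, for example, are CD19+ and negative for CD3, CD16 and CD56. For T cells it gives the parent populations (CD3+, CD4+, CD8+) and then, separately and labelled as activated, CD8+ HLADR+. NK and NKT cells have no parent line and no activated label. The CD107+ phenotype is their only entry.

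**What the literal rule counts.** Let N be the number of CD3-, CD16+/CD56+ cells and f the share of them that is CD107+.

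- Reported count R = N × f, with f between 0 and 1. R equals N only if f = 1.
- Between two visits, R2/R1 = (N2/N1) × (f2/f1). A change in R therefore cannot be assigned to N or f from R alone.

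**Illustration on assumed values.** The documents give neither N nor f.

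- With N = 200/uL, f = 0.01 gives R = 200 × 0.01 = 2/uL, and f = 0.30 gives R = 200 × 0.30 = 60/uL.
- If N falls from 200 to 100/uL while f rises from 0.02 to 0.08, R goes from 200 × 0.02 = 4/uL to 100 × 0.08 = 8/uL. The reported count doubles while the true count halves.
- In general R moves against N after a fall whenever f2/f1 exceeds N1/N2. Here 0.08/0.02 = 4 exceeds 200/100 = 2. These values were chosen to show that a reversal is possible; they say nothing about how likely it is.

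**CD3 in 6.4.4 item 4.** Under 6.2.3 an NKT cell is CD3+ and CD56+. A CD107+ NKT cell therefore meets the condition CD56+, CD107+ and falls inside the NK activity gate as written.

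**The slash.** Section 6.2.3 requires CD16 and CD56 together. The slash in 11.2.4 could mean both, or either. If it means either, the two populations differ even with CD107 removed.

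**The case against.** The strongest reply has four parts.

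1. *The bracket may list markers to be stained.* Item 1 asks for subsets to be monitored, and the detailed gating may sit in the correlative lab manual named in 6.4.2, which is not available here. This is possible, but the signed phenotypes and the T-cell parent lines make it the weaker reading. If it was meant, the text still needs correcting.

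2. *The total count can be obtained.* Section 6.4.4 item 2 lists CD3, CD16, CD56 and CD107 as separate antibodies, so the parent population is stained. This stands. A reader might infer that number and activation cannot be separated at all in this trial. The documents do not support that: the parent count is available from the same panel, but 11.2.4 does not ask for it.

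3. *No comparison with the infused product is planned.* This also stands. A reader might infer that a dose-recovery analysis fails because of CD107. No such analysis appears anywhere, and of the infused NK and NKT content 6.2.3 says only that it is monitored, "but the infusion dose will be calculated around CD3+ population". Removing CD107 would not make the two figures directly comparable either: 6.2.2 expects autologous recovery and 12.1 expects no long-term engraftment, so the recovering NK cells would be mainly the patient's own.

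4. *The 6.4.4 item 4 gate may be shorthand.* Item 1 of 11.2.4 does separate CD3- from CD3+ cells, and CD3 is in the panel. So the documents do not show that NKT cells will be counted as NK activity, only that the written gate does not exclude them.

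A reader might also take this as a flaw in the test of the trial's main mechanism. The protocol hedges on NK cells, also proposes maternal-fetal microchimerism, and in 3.7 credits infused donor lymphocytes in general. The item 4 assay, KIR typing and the KIR-ligand subgroup analysis in 11.3 are unaffected.

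**Conclusion.** The point holds as an inconsistency of definition. Section 11.2.4 promises NK enumeration and then states a rule that, followed literally, counts only the CD107+ part of the NK and NKT cells. The definition also differs from that in 6.2.3, and the activity gate in 6.4.4 item 4 omits CD3.

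The size of the undercount is the unknown factor f, between 0 and 1; the documents support nothing narrower. The conclusion rests on reading item 1 as a set of phenotypes, as its other entries indicate, and on taking CD107 as an activity marker, as the protocol itself does.

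The impact is minor. The analysis consists of tables and plots in at most 21 evaluable subjects, with no test, stopping rule or sample size attached. The definition should still be corrected, because as written it changes what a reported secondary result means.

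**What to change.** - In 11.2.4 item 1, define NK cells as CD3- and NKT cells as CD3+, each with the CD16/CD56 condition and without CD107.
- Use one CD16/CD56 rule in 6.2.3 and 11.2.4, and say whether both markers or either one is required.
- Report the CD107+ percentage of those cells separately, as the functional read-out.
- In 6.4.4 item 4, state CD3- in the NK activity gate so that CD3+ CD56+ cells are excluded.
- Bring the correlative lab manual into line if its gating differs.

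The cost is a few lines of text. CD3, CD16, CD56 and CD107 are all in the 6.4.4 panel, so no new assay is needed. If samples have already been run, whether they can be re-gated depends on whether the flow files were kept, which the documents do not say.
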